## **E2 Subject Selection and Withdrawal**

### **2.a Inclusion Criteria**

- 18 years of age or older
- diagnosis of uveitis
- for patients with uveitis (documented in medical record):
  - prior treatment failure with adalimumab
  - medical contraindication to adalimumab
  - patient unable or unwilling to perform self-injections
  - patient unable to obtain adalimumab due to cost or insurance
- a clinical response to steroids
- active disease requiring at least 10mg of prednisone (or steroid equivalent) for 2 or more weeks
  - active disease is defined as any of the following
    - at least one active inflammatory chorioretinal or retinal vascular lesion
    - anterior chamber cell grade of 2+ or higher (according to Standardization of Uveitis Nomenclature Working Group criteria)
    - vitreous haze grade of 2+ or higher (according to National Eye Institute [NEI] criteria adapted by the Standardization of Uveitis Nomenclature Working Group)
- practice of preventative contraception for women of childbearing age

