### **2.a Exclusion Criteria**

- presence of an active or uncontrolled systemic rheumatologic disorder
- suspected or confirmed ocular infection
- chronic or recurring infections, such as HIV
- renal insufficiency, which would preclude safe administration of tofacitinib

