## **2.i Cessation of tofacitinib therapy**

### **i Indications for cessation of tofacitinib therapy**

- Laboratory abnormalities:
  - New elevation of ALT or AST > 3x upper limit of normal
  - New leukopenia with ANC < 1.5
  - New anemia with hemoglobin <7 g/dl or a decrease of > 3g/dl
  - New renal failure that would preclude the safe administration of tofacitinib
    - Patients may restart tofacitinib after recovery of renal function
- Clinical events:
  - Shingles or opportunistic infection:
    - Patients that develop an opportunistic infection or shingles may opt to (1) withdraw from the study or (2) hold tofacitinib while undergoing treatment with antivirals or antibiotics
  - Hospitalization due to tofacitinib
    - Any patient hospitalized secondary to treatment with tofacitinib as determined by a rheumatology research clinician.
  - Infection with tuberculosis:
    - Patients that develop active mycobacterium tuberculosis. All patients will have undergone screening with a PPD or interferon gamma release assay to rule out TB at the beginning of the study.
  - Treatment failure after week 8

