### ***F3 Initial Visit (week 0; baseline)***

- Informed consent
- Inclusion/Exclusion criteria verification
- Medical history and Demographics
- Concomitant Medication collection
  - Dose of medications used to treat increased intraocular pressure
  - Dose of topical and/or systemic corticosteroids
- Ophthalmology data
  - Anterior chamber cell
  - Vitreous haze
  - Retinal lesions
  - Visual Acuity
  - Cystoid macular edema
  - Intraocular pressure
- Provide Subject Study Handout
- Provide Drug Package Insert
- Dispense Study Drug

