## L Attachments

### L1 Tables

Table 1. Schedule of Laboratory measurements

	Week					
	0	4	8	12	16	24
Clinic visit	X	X	X	X	X	X
CMP & CBC	X	X		X		X
Lipid Panel	X					X
Hepatitis B	X					
Hepatitis C	X					
PPD / IGRA*	X					

\*IGRA: Interferon-gamma release assay a.k.a. T spot for TB

Patients with Hepatitis B & C serologies within the past 5 years will not need repeat labs.

Patients with a PPD / IGRA in the past 12 months will not need repeat labs.

Table 2. Oral steroid (prednisone or equivalent) taper

Week	Prednisone dose (mg/day)
0	60
1	60
2	50
3	40
4	30
5	20
6	15
7	12.5
8	10
9	7.5
10	5
11	4
12	3
13	2
14	1
15	0

Table 3. Prednisone Drop Taper Schedule – patient-specific wherever they start

Dose (# of drops/day) per Week
--------------------------------

12
10
8
6
5
4
3
2
1

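### The only reproductive safeguard is reported contraception: no pregnancy test is scheduled before drug is dispensed, so an unrecognised pregnancy would go undetected

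*Combined protocol and SAP*

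**What the plan says.** The inclusion criteria in section 2.a admit patients who are "18 years of age or older", with no upper age limit and no restriction by sex, so women of childbearing age are eligible. For them the section adds "practice of preventative contraception for women of childbearing age". It gives no method of contraception, no duration and no means of verification.

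The exclusion criteria are four: "presence of an active or uncontrolled systemic rheumatologic disorder", "suspected or confirmed ocular infection", "chronic or recurring infections, such as HIV", and renal insufficiency that makes tofacitinib unsafe.

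The week 0 visit in F3 lists "Inclusion/Exclusion criteria verification", medical history, handover of the package insert and dispensing of study drug, all at the same visit. Section F2 refers laboratory work to Table 1, titled "Schedule of Laboratory measurements". Section 2.i sets out the "Indications for cessation of tofacitinib therapy". Section L2 refers to a separate consent document.

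**The concern.** By asking for contraception, the protocol itself treats pregnancy on study drug as something to avoid. The criterion, however, concerns behaviour and not pregnancy status. Nothing else in the plan closes that gap: there is no test before the first dose, no later question about contraception, and no statement of what happens if a pregnancy occurs.

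What is at stake is the safety of an individual participant. If staff follow the protocol exactly, a pregnancy that the patient does not know about is not detected before she takes the drug. If a pregnancy becomes known during the study, the protocol gives no instruction on study drug or follow-up.

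**Working it through.** No formula applies and the plan states no figure to reproduce. The check is to read each place where a pregnancy safeguard could sit and record what is there.

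- **Inclusion criteria (2.a):** one line, on contraceptive practice. Pregnancy status is not mentioned.
- **Exclusion criteria (2.a):** 4 items (rheumatologic disorder, ocular infection, chronic infection, renal insufficiency). Pregnancy items: 0 of 4.
- **Table 1:** 5 laboratory rows (CMP and CBC, lipid panel, hepatitis B, hepatitis C, PPD or IGRA). Pregnancy tests: 0 of 5, at any week.
- **F3, week 0:** eligibility verification and dispensing are both listed, with no pregnancy test among the procedures.
- **F4, later visits:** concomitant medication, eye data, adverse events and drug accountability. There is no contraception question and no test.
- **2.i, reasons for stopping:** 4 laboratory criteria (liver enzymes, neutrophils, hemoglobin, renal failure) and 4 clinical events (shingles or opportunistic infection, hospitalization due to the drug, tuberculosis, treatment failure after week 8). Pregnancy items: 0 of 4 and 0 of 4, so 0 of 8.
- **2.j (dose reduction), 2.e (risks) and 5.c (adverse event examples):** pregnancy is not named.

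Next, follow one patient through the text. A woman in early pregnancy, unaware of it, reports that she uses contraception. She satisfies the contraception line and meets none of the 4 exclusions. Verification at week 0 confirms what the criteria ask. None of the scheduled blood tests is a pregnancy test. She leaves the visit with study drug. At weeks 4, 8, 12, 16 and 24 no listed procedure asks about contraception or tests for pregnancy.

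Finally, compare this with how the protocol treats other hazards that it recognises:

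- Tuberculosis has a baseline test in Table 1, a statement in 2.i that all patients are screened, and a stopping rule.
- Renal impairment has an exclusion, a metabolic panel at weeks 0, 4, 12 and 24, a stopping rule and a dose-reduction line.
- Pregnancy has one line of reported behaviour.

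The gap is visible against the protocol's own standard and needs no outside source.

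**The case against.** The strongest reply is that the criterion already does most of the work. A woman who knows that she is pregnant would ordinarily not be practising contraception and would arguably fail inclusion. The week 0 visit also includes a medical history, informed consent and the package insert, and specialists manage the treatment. This stands in part. A reader might infer that any pregnant woman can be enrolled; the documents do not support that. History can confirm contraceptive practice, which is what the criterion asks, but it cannot exclude a pregnancy that the patient does not know about.

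The consent form and the insert were not available for review and may contain instructions on pregnancy. That limit is real, but neither would be a protocol criterion or a scheduled test.

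Four further inferences are tempting and should not be drawn:

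- **Length of exposure.** Adding the 24 weeks to the possible one-year extension gives a maximum treatment duration, not a fetal exposure. The extension is only potential and is confined to responders.
- **Added conventional agents.** A reader might count these as a further hazard created by the trial. Under E1 and 3.f those patients were already on the agent, and the documents state no reproductive risk for it.
- **A contradiction between 2.a and 2.i.** There is none. Section 2.i is silent.
- **The size of the harm.** D3 and 2.e list no fetal risk for tofacitinib. The contraception criterion supports saying that its purpose is not verified, and supports no estimate of harm.

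It is also fair to say that the trial is small, that there may be no women of childbearing age in it, and that no endpoint is affected. This limits the scale of the point but does not remove it, because the risk falls on an individual and does not depend on statistical power.

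**Conclusion.** The point holds for unrecognised pregnancy and contraceptive failure. A woman in either position who reports contraception meets every written criterion, and no scheduled procedure would detect the pregnancy before she receives drug at week 0 or afterwards.

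The size is 0 pregnancy items in the 4 exclusions, the 5 laboratory rows and the 8 stopping criteria. The number of patients affected cannot be derived: enrolment is at most 5, and the share who are women of childbearing age is not stated, so the range is 0 to 5.

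The conclusion assumes that Table 1 is the complete laboratory schedule, as F2 indicates, and that the pages not available for review, including the consent form, add no scheduled test. It does not touch the sample size, the endpoint or the descriptive analysis. It is a cheap improvement in patient safety.

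**What to change.** - In Table 1 (week 0 column) and in F3, add a pregnancy test for women of childbearing age, with the result available before study drug is dispensed.
- In F4, add a check of contraception at each later visit.
- The sponsor should reconcile the inclusion and exclusion criteria in 2.a with section 2.i, so that the protocol states how pregnancy status bears on eligibility and how a pregnancy on study is handled and followed. The content of those rules is for the sponsor; none is proposed here.

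The cost is one amendment, one inexpensive test and one question per visit for the patients concerned, among at most 5 enrolled. The test can be done on urine or on the blood already drawn at week 0 for the scheduled panels.

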### **2.a Exclusion Criteria**

- presence of an active or uncontrolled systemic rheumatologic disorder
- suspected or confirmed ocular infection
- chronic or recurring infections, such as HIV
- renal insufficiency, which would preclude safe administration of tofacitinib

### **2.b Ethical Considerations**

There is one FDA-approved steroid-sparing therapy for uveitis (adalimumab). Tofacitinib and adalimumab are equally effective in treating the associated systemic disorder, psoriatic arthritis. For patients who have failed adalimumab, tofacitinib offers a reasonable alternative therapy.

Patients will have regular follow-up with both Ophthalmology and Rheumatology to monitor disease activity. Treatment with corticosteroids will be available for rescue therapy for all patients with uncontrolled disease.

Patients may be influenced to participate because an authority figure (their physician) may propose the study, however, steps that will be taken by the research team to minimize the possibility of coercion or undue influence during the consent process. The consent process will include full study disclosure, giving the patient a reasonable amount

---

of time to decide regarding participation and the opportunity to discuss with family and friends, and assuring the patient that they will receive the same quality of care regardless of study participation.

## **2.c Subject Recruitment Plans and Consent Process**

Patients seen in the clinical offices of the Department of Ophthalmology & Visual Sciences and the Division of Rheumatology at Washington University will be consented in a private room within the clinical office.

## **2.d Randomization Method and Blinding**

There is no randomization or blinding in this study.

## **2.e Risks and Benefits**

As with other immunosuppressive treatments to control autoimmune diseases, the patients will be at increased risk of infection (20%). Other risks include nasopharyngitis (3% to 14%), hypertension (2%), headache (4% to 9%), rash (6%), acne vulgaris ( $\geq 2\%$ ), increased serum cholesterol (5% to 9%), diarrhea (4% to 5%), gastroenteritis (4%), nausea (4%), urinary tract infection (2%), anemia (4%), herpes zoster infection (5%; including disseminated cutaneous, meningoencephalitis, ophthalmologic), increased creatine phosphokinase (3% to 7%), increased serum creatinine ( $< 2\%$ ), upper respiratory tract infection (4% to 6%), and fever ( $\geq 2\%$ ).

Lymphoma and other malignancies have been reported in patients receiving tofacitinib

Tuberculosis (pulmonary or extrapulmonary) has been reported in patients receiving tofacitinib. Standard laboratory screening is performed in all patients to assess for latent / chronic infection, such as TB.

There is a risk associated with lack of efficacy. In the case of a treatment failure based on the primary outcome criteria, tofacitinib will be discontinued and the patient will be switched to an alternative steroid-sparing therapy at the discretion of the patient's treating physician.

Potential benefits include improved control of the ocular inflammatory disease, reduced corticosteroid usage, reduced intraocular pressure, improved visual acuity, and prevention of permanent vision loss. The participants may also derive benefit from contributing to medical research.

## **2.f Early Withdrawal of Subjects**

Participants may withdraw at any time from the study. They will be asked to undergo an Early Exit Visit.

## **2.g When and How to Withdraw Subjects**

Participants will contact the researcher if they wish to withdraw.

## **2.h Data Collection and Follow-up for Withdrawn Subjects**

Participants who withdraw will no longer be followed in the study.

---

## **2.i Cessation of tofacitinib therapy**

### **i Indications for cessation of tofacitinib therapy**

- Laboratory abnormalities:
  - New elevation of ALT or AST > 3x upper limit of normal
  - New leukopenia with ANC < 1.5
  - New anemia with hemoglobin <7 g/dl or a decrease of > 3g/dl
  - New renal failure that would preclude the safe administration of tofacitinib
    - Patients may restart tofacitinib after recovery of renal function
- Clinical events:
  - Shingles or opportunistic infection:
    - Patients that develop an opportunistic infection or shingles may opt to (1) withdraw from the study or (2) hold tofacitinib while undergoing treatment with antivirals or antibiotics
  - Hospitalization due to tofacitinib
    - Any patient hospitalized secondary to treatment with tofacitinib as determined by a rheumatology research clinician.
  - Infection with tuberculosis:
    - Patients that develop active mycobacterium tuberculosis. All patients will have undergone screening with a PPD or interferon gamma release assay to rule out TB at the beginning of the study.
  - Treatment failure after week 8

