## **2.j Adjustment of tofacitinib therapy**

### **i Indications for dose reduction of tofacitinib therapy to 5mg daily**

- moderate to severe renal impairment
- ESRD requiring hemodialysis
- moderate hepatic impairment

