### **5.c Definitions of Adverse Events**

Any unfavorable medical occurrence in a human subject including any abnormal sign, symptom, or disease.

Some possible adverse event include:

1. Drug Reaction
  - This includes a rash, drug hypersensitivity or allergic reaction.
2. Laboratory abnormality
  - Elevation of ALT, AST, or creatinine on complete metabolic panel above baseline and three times above the upper limit of normal
  - Decrease of white blood cell count, absolute neutrophil count, hemoglobin, platelet count below baseline and below the normal range
  - Increase of blood lipid and cholesterol levels above baseline and above the normal range
3. Infection
  - This includes bronchitis, influenza, nasopharyngitis, pharyngitis, rash, upper respiratory tract infection, and urinary tract infection.
4. Malignancy
  - Any new diagnosis of malignancy during the study period will be recorded.
5. Hospitalization
  - Any hospitalizations during the study period and the primary diagnosis for hospitalization will be recorded.

---

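### Three laboratory stopping values (ALT/AST, ANC, haemoglobin) have no matching entry limit, and because they apply only to undefined 'new' abnormalities, a stable baseline abnormality may meet no written stopping rule

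*Combined protocol and SAP*

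**What the plan says.** Section 2.i, on stopping tofacitinib, gives four laboratory indications. Three carry numbers: "New elevation of ALT or AST > 3x upper limit of normal", "New leukopenia with ANC < 1.5" and "New anemia with hemoglobin <7 g/dl or a decrease of > 3g/dl". The fourth is new renal failure severe enough to make the drug unsafe. All four depend on the abnormality being new, and the term is not defined.

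At entry, the only organ-function criterion is the exclusion for "renal insufficiency, which would preclude safe administration of tofacitinib", which has no number. Neither the inclusion nor the exclusion list mentions liver enzymes, neutrophils or haemoglobin.

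Table 1 in L1 schedules CMP and CBC at weeks 0, 4, 12 and 24. E1 says this laboratory monitoring follows standard of care for detecting drug toxicity. F3 lists verification of the entry criteria and "Dispense Study Drug" at the same week 0 visit, and it does not name the laboratory result as a condition.

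**The concern.** The plan itself treats these three values as reasons to stop a patient who is on the drug. One would expect the same values to bar a patient from starting, or at least to trigger a written decision at week 0. For renal function the plan does pair a stopping rule with an entry rule. For liver enzymes, neutrophils and haemoglobin it does not.

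At stake is individual patient safety. Section 2.e lists infection (20%) and anemia (4%) among the risks. Under E1 and 3.f, some patients take tofacitinib on top of a conventional immunosuppressant, and all start prednisone at 60 mg daily. If a candidate arrives already past one of the limits, protection rests on the clinician's judgement and not on a rule.

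**Working it through.** No power or precision calculation applies, so the check sets the rules side by side.

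**Step 1: count the entry criteria.** At top level the inclusion list has 6 (age, diagnosis, adalimumab status, steroid response, active disease on at least 10 mg prednisone, contraception). The exclusion list has 4 (systemic rheumatologic disorder, ocular infection, chronic or recurring infection, renal insufficiency). 6 + 4 = 10, of which 0 name ALT/AST, ANC or haemoglobin.

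**Step 2: match stopping rules to entry rules.**

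| Laboratory stopping rule (2.i) | Entry counterpart (2.a) |
|---|---|
| ALT/AST > 3x ULN, if new | none |
| ANC < 1.5, if new | none |
| Haemoglobin < 7 g/dl, if new, or a fall > 3 g/dl | none |
| Renal failure, if new | renal insufficiency, no number |

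Of 4 rules, 1 has a counterpart, so 4 - 1 = 3 have none.

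**Step 3: follow an example patient.** Take a candidate with ANC 1.2 or ALT 3.5x ULN at week 0 who meets all other criteria.
- Eligibility: no criterion is breached, so the patient qualifies.
- Dispensing: F3 allows it at the same visit without the result, and F1 requires only that consent be signed before drug is given.
- Stopping, if 'new' means new since baseline: a stable value does not meet 2.i.
- Stopping, if 'new' means newly detected: an abnormality first found on the week 0 draw does meet 2.i, though drug may already have been dispensed.

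The gap at entry exists on either reading. The gap in stopping depends on the first.

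**Step 4: look for another rule that closes the gap.**
- 2.e: "Standard laboratory screening is performed in all patients to assess for latent / chronic infection, such as TB". This screening has a different purpose.
- 2.j: the dose falls to 5 mg daily for "moderate hepatic impairment". This can apply from baseline, but it neither withholds nor stops drug, is not defined by ALT/AST, and does not concern ANC or haemoglobin.
- 5.c: the liver-enzyme example of an adverse event is a value "above baseline and three times above the upper limit of normal". The blood-count example is likewise relative to baseline. These are non-exhaustive examples for recording events, not dosing rules. Their use here is only that they favour reading 'new' as new since baseline.
- E1, 5.a, 5.e and I1: toxicity monitoring, safety monitoring and laboratory review at visits, and weekly investigator review. None states a threshold or an action.
- G2: a rule for stopping the whole trial, not for one patient.
- 2.i, haemoglobin: the fall of more than 3 g/dl could catch a patient who starts low and then drops, but not a stable one.

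No section was found that withholds or stops drug for a stable value already past one of the three limits.

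**The case against.** The best defence is that this is a single-site, open-label, descriptive pilot of at most 5 patients (G1) run by specialists. E1 gives the scheduled laboratory tests a stated toxicity purpose, and I1 has the investigators reviewing data, laboratory results included, every week. A week 0 abnormality would probably be seen within about a week. The renal exclusion is also left to judgement, so relying on clinicians is consistent with the plan's style. Harm needs several things together: a candidate past a limit, a specialist who sees the value and still doses, the treatment-emergent reading of 'new', and a value that stays put.

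All of this stands as an argument about size. It does not supply the missing rule.

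A reader might infer that the plan definitely keeps such a patient on drug. The documents do not support that: 'new' is undefined, the newly-detected reading is possible, and any clinician may decline to treat. Nor do they support the inference that week 0 results go unexamined.

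The defence is also right that the remedy is not free, since F3 puts consent, eligibility and dispensing in one visit.

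**Conclusion.** The concern holds in this form. Three of the four laboratory stopping values have no entry counterpart, and the week 0 result need not be known before drug is dispensed. A patient already past one of them is eligible. If 'new' means new since baseline and the value is stable, that patient meets no written stopping rule.

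The conclusion on stopping rests on that reading of 'new', which is natural but undefined. The conclusion on eligibility does not.

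The size is modest. At most 5 patients are exposed and they are closely reviewed. The documents give no rate of baseline abnormality, so no probability of harm can be stated, and a claim that harm is likely would go beyond them. No endpoint or analysis is affected. This is a cheap improvement, not a flaw that undermines the trial.

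**What to change.** 1. Add to the Exclusion Criteria in 2.a: ALT or AST > 3x ULN, ANC < 1.5 (with its unit), or haemoglobin < 7 g/dl, on the week 0 CMP/CBC or on a recent prior result within a stated number of days. The clinicians may prefer stricter limits, since a candidate at, say, ALT 2.9x ULN could cross the stopping value after a trivial rise.
2. In F3, require that result to be checked against the limits before drug is dispensed.
3. If a prior result may be used for entry, state in 2.i that the three limits apply whatever the baseline value. If only the week 0 result is used, any later value past a limit is new by construction and this sentence is not needed.

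The cost is a short amendment to 2.a and F3, and possibly one sentence in 2.i. No new test is needed, because CMP and CBC are already scheduled at week 0. The downside is that dispensing may have to wait for the result, perhaps at the price of an extra visit for a patient with active disease. Accepting a recent prior result limits that delay. An occasional candidate will be excluded.

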### **A2 Primary Hypothesis**

Treatment with tofacitinib will limit ocular inflammation in the after steroids have been tapered off.

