### **ii Monitoring after tofacitinib cessation**

- If a patient is not a treatment failure as defined by the primary outcome measure at the time of tofacitinib cessation, they will be monitored for disease relapse
- If a patient is a treatment failure at the time of tofacitinib cessation, they will be switched to another steroid sparing agent at the discretion of their treating physician
- Patients who discontinue tofacitinib treatment will remain in the study and be followed to obtain safety data.

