### **3.f Prior and Concomitant Therapy**

All patients will be prescribed steroids with a uniform and pre-determined taper starting at prednisone 60mg daily (or equivalent) and tapering over 14 weeks to off.

Patients intolerant to an initial steroid-sparing therapy (e.g. methotrexate, azathioprine, or mycophenolate) will be started on tofacitinib and their prior steroid-sparing therapy will be discontinued. No other steroid sparing therapy will be initiated during the study period to avoid confounding of clinical efficacy.

Patients tolerant to prior steroid sparing therapy but with an incomplete control of their disease will have tofacitinib added to their steroid-sparing therapy. No other steroid sparing therapy will be initiated during the study period to avoid confounding of clinical efficacy.

Concomitant therapy with biologic steroid-sparing therapy such as adalimumab is prohibited due to the risk of infection.

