### **G3 Analysis Plan**

All analysis will be descriptive. We expect 40-60% of patients to meet the primary endpoint in each arm similar to adalimumab in the treatment of noninfectious uveitis. This is in contrast to the placebo arm, which had a treatment failure rate of 80% at 24 weeks (12).

Patients will be analyzed by intent to treat when all 5 patients in a treatment arm have either completed 6 months of therapy or discontinued therapy due to study withdrawal or indications for treatment cessation.

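### For shingles or opportunistic infection, the protocol offers leaving the study as event management, which ends the follow-up that section 2.i.ii gives to patients who stop tofacitinib

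*Combined protocol and SAP*

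**What the plan says.** Section 2.i, part i (indications for cessation) of the combined protocol and SAP lists shingles or opportunistic infection as a reason to stop tofacitinib. It adds that affected patients "may opt to (1) withdraw from the study or (2) hold tofacitinib while undergoing treatment with antivirals or antibiotics". No other indication in that list (laboratory abnormalities, hospitalization due to the drug, tuberculosis, treatment failure after week 8) names study withdrawal as an option.

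Section 2.h gives the consequence of option (1): "Participants who withdraw will no longer be followed in the study". Section 2.f asks a withdrawing participant for an Early Exit Visit and already allows withdrawal at any time.

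Section 2.i, part ii, sets the general rule for stopping the drug: "Patients who discontinue tofacitinib treatment will remain in the study and be followed to obtain safety data". Patients who have not failed when they stop are also watched for relapse.

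Section G3 plans an intent-to-treat analysis. It is triggered once each patient has completed 6 months or "discontinued therapy due to study withdrawal or indications for treatment cessation", so it names the two routes separately. Section G5 censors patients with a missing primary outcome in the initial efficacy analysis.

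**The concern.** Stopping the drug and leaving the study are different things, and the protocol keeps them apart everywhere except here. For this one type of event, a clinician who follows 2.i.i literally would put leaving the study to the patient as one of two ways to deal with the infection. Stopping for good while staying under observation is not on the list, and no reason is given for the exception.

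Two things are at stake for a patient who takes option (1). The first is safety: the later course of the infection is no longer observed in the study. Section 2.e describes zoster as including disseminated, meningoencephalitic and ophthalmologic forms, so that course matters in an eye trial. The second is efficacy: unless the patient has already failed under C1, status at week 24 is unknown.

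**Working it through.** The documents give no figure to reproduce here. The check compares the sections and counts visits.

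**Side by side**

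| Route | Governing section | What follows |
|---|---|---|
| Stops tofacitinib for any listed indication | 2.i.ii | Stays in the study; safety follow-up; relapse monitoring if not a failure |
| Shingles or opportunistic infection, option (1) | 2.i.i, then 2.f and 2.h | Early Exit Visit requested; no further follow-up |
| Shingles or opportunistic infection, option (2) | 2.i.i | Drug held; restart neither required nor excluded |

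For renal failure, by contrast, the same list does address restarting: "Patients may restart tofacitinib after recovery of renal function". A patient who takes option (2) and never restarts can be read as covered by 2.i.ii. The gap is therefore confined to option (1).

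**Visits lost**

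Inputs: post-baseline visits at weeks 4, 8, 12, 16 and 24, so 5 visits (F2). Prednisone by week is 15 mg at week 6, 5 mg at week 10, 1 mg at week 14 and 0 at week 15 (L1, Table 2). Section 3.f describes the same taper as "tapering over 14 weeks to off". Visits at nominal week 15 or later are weeks 16 and 24, so 2 of 5 are off oral steroid.

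| Exit | Scheduled visits left | Scheduled off-steroid visits lost | Prednisone at the exit visit |
|---|---|---|---|
| Between weeks 4 and 8 | 4 | 2 of 2 | 15 mg if at week 6 |
| Between weeks 8 and 12 | 3 | 2 of 2 | 5 mg if at week 10 |
| After week 12, before week 15 | 2 | 2 of 2 | 1 mg if at week 14 |
| Week 15, before the week 16 visit | 2 | 2 of 2 | 0 |
| After the week 16 visit | 1 | 1 of 2 | 0 |

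F4 gives the Early Exit Visit the same eye measurements and adverse event collection as a scheduled visit. If attended at week 15 or later, it is itself an assessment off oral steroid, though not of week-24 status. Only an exit before week 15 leaves no such assessment.

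This assumes that the taper runs as scheduled and visits fall on their nominal week. With the window of 2 weeks either side, the week 16 visit could fall at week 14, on 1 mg.

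**Share of the sample**

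G1 allows at most 5 patients, so one withdrawal is at least 1/5 = 20%. As an illustration, suppose 5 are enrolled, one leaves before failing, and 2 of the other 4 fail. If G5's censoring means exclusion from the proportion, the result is 2/4 = 50%. With all five known it would be 2/5 = 40% or 3/5 = 60%, which are the two ends of the range that G3 expects.

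**Likelihood**

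Not estimated. The 5% zoster figure in 2.e has no time base, and the share of patients who would choose option (1) is not given.

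**The case against.** The strongest reply is that 2.i.ii sits directly below the disputed text and has no exception, so a patient who holds the drug and stays off it remains in follow-up. This stands. A reader might infer that the protocol forbids permanent discontinuation with follow-up after shingles; it does not. It only leaves that route off the list and puts study withdrawal on it.

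Second, option (1) is the patient's choice and creates no right that 2.f does not already give. That also stands, and nothing shows that the wording would steer patients out. But a general right to leave is not the same as listing departure as one of two responses to an adverse event.

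Third, the loss is limited. The exit visit, if attended, records eye findings and adverse events. Section 5.h leaves later events to routine care. A failure before exit is already known. All of this is correct.

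Fourth, the primary hypothesis is "Treatment with tofacitinib will limit ocular inflammation in the after steroids have been tapered off". A patient who has stopped the drug for good says little about it at weeks 16 and 24. A reader might infer that the change would recover evidence of tofacitinib's steroid-sparing effect. It would not: the efficacy gain is a known outcome for the intent-to-treat analysis. Even that is conditional, because the G3 trigger does not wait for week 24 in a patient who has discontinued.

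**Conclusion.** The point holds as a narrow inconsistency. For one type of safety event, 2.i.i offers a route that ends in-study follow-up, while 2.i.ii keeps patients who stop the drug under observation. Each patient who takes it is 1 of at most 5. That patient loses in-study follow-up of the infection beyond the requested exit visit, loses relapse monitoring and, if not already a failure, has no week-24 status. Under G5 the patient is then censored in the initial efficacy analysis, which sits poorly with the intent to treat in G3.

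Two further inferences would go too far. One is that safety counts are compromised: the case is recorded when it occurs, so incidence and the G2 stopping rule (3 or more shingles cases on drug) are unaffected. The other is that every such exit removes the assessment after the steroid taper: by the nominal schedule, that is true only before week 15.

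The study is a descriptive pilot and no decision rule depends on this. It is worth considering because the remedy is cheap, not because the effect is large.

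**What to change.** In 2.i.i, under shingles or opportunistic infection, change option (1) to: discontinue tofacitinib permanently and remain in the study under 2.i.ii through week 24. Keep the hold option, and add that 2.i.ii applies if the drug is not restarted. State there that the right to withdraw at any time under 2.f is unchanged. Section 2.h needs no edit, since it already concerns only participants who withdraw.

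The cost is a small wording change and a few extra records from visits that are already scheduled and that F2 describes as standard of care. No follow-up past week 24 is added, and patients lose no choice. Because they stay free to leave, the change makes continued follow-up the offered course but cannot guarantee the data.
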